Spinal excitability measurements: <= 25 single PNS pulses to the left wrist at <= 120% of M-max. Measurements will be taken immediately before PCMS and at 0, 20 and 40 minutes after PCMS.

Voluntary motor output measurements: <= 5 maximum voluntary contractions of the FDI, each lasting <= 5 seconds. Measurements will be taken immediately before PCMS and at 0, 20 and 40 minutes after PCMS. Manual dexterity measurements. <= 5 attempts of the 9-hole peg test. Measurements will be taken immediately before PCMS and at 0, 20 and 40 minutes after PCMS.

5 Data Analysis

Describe the data analysis plan, including any statistical procedures or power analysis. To input text, click in the light grey area below.

Experiment 1:

- 1. Primary outcome: Amplitude of MEPs evoked during brain states reflecting strong, weak, and/or random corticospinal tract recruitment
 - a. This outcome will be evaluated using linear-mixed effects models (fixed effect of state, random effect of subject) with alpha equal to 0.05.

Experiment 2:

- 1. Primary outcome: amplitude of FDI muscle response after TST application during brain states reflecting strong, weak, and random corticospinal tract recruitment.
- 2. Secondary outcome: area under the curve of FDI muscle response after TST application during brain states reflecting strong, weak, and random corticospinal tract recruitment.
 - a. Both outcomes will be evaluated using linear mixed-effects models (fixed effect of state, random intercept of subject) with alpha equal to 0.05.

Experiment 3:

- 1. Primary outcomes: Maximum FDI force output, FDI activation (calculated using the root-mean-square of EMG signals obtained during FDI contractions)
- 2. Secondary outcome: Number of pegs placed per attempt at the 9-hole Pegboard test.
- 3. Exploratory outcomes: Amplitudes of MEPs produced by scalp TMS, amplitudes and persistence of Fwaves evoked by wrist PNS
 - All outcomes will be evaluated before and after PCMS. Outcomes will be analyzed using linearmixed effects models (fixed effects of condition and time point, random intercept of subject).
 Main effects will be evaluated using likelihood ratio tests, and p-values from post-hoc contrasts will be corrected for multiple comparisons. Alpha will be equal to 0.05.

STUDY ELEMENT IDENTIFICATION

6 Study Elements

Click on the check box (or double click and type an "X" if using Google Docs) each procedure included in your study.

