- Single-pulse TMS pulses will be delivered during EEG and EMG recordings. Immediately afterwards, EEG and EMG data will be analyzed using machine learning. The brain states identified using machine learning will be used for subsequent real-time EEG analysis.
- The M-max following PNS at the wrist will be determined by increasing stimulation intensity until a larger response cannot be obtained. EMG signals may be recorded for offline quality control analysis.
- Electrode positions may be marked on the skin using a skin-safe surgical marker to ensure consistent electrode placement across sessions.
- Single-pulse TMS to the scalp and wrist PNS will be performed to calculate delays needed for PCMS (see Design and Methodology). EMG signals will be recorded to enable delay calculation.
- Delays for PCMS application will be calculated using the following formulas (units are milliseconds; Bunday and Perez 2012; Urbin et al. 2021):
 - Peripheral Conduction Time (PCT) = (F-wave latency –M-wave latency) * 0.5
 - Central Conduction Time (CCT) = MEP latency (PCT + M-wave latency)
 - Active PCMS Delay = (PCT CCT) X ms (where X = 1 5 ms)
 - \circ Control PCMS Delay = (PCT CCT) + X ms (where X = 5 30 ms)
- The real-time EEG analysis algorithm will be used to deliver TMS pulses during the target brain state for that session. The order of brain states targeted per session will be counterbalanced across subjects. During this time, participants will rest quietly with their eyes open (Zrenner et al. 2018; [name] et al. 2020). EEG and EMG data will be recorded for offline quality control analysis.

- Participants will complete pre-PCMS measurements of corticospinal excitability, spinal excitability, voluntary motor output, and manual dexterity (see Design and Methodology). EMG signals will be recorded during all measurements and processed offline to obtain outcome measures. EEG may recorded for offline quality control analysis.
- The PCMS intervention will be delivered (see Design and Methodology) during the target brain state for that session. The order of brain states targeted per session will be counterbalanced across subjects. EEG and EMG signals will be recorded for subsequent quality control analysis.
 - Active PCMS during brain states reflecting strong corticospinal recruitment, with the delay between scalp TMS and wrist PNS equal to the Active PCMS delay.

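### The EMG-based primary outcomes have no stated scaling, and in Experiment 3 the written model lets day-specific electrode gain into the condition comparison

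*Combined protocol and SAP*

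**What the plan says.** Section 5 (Data Analysis), Experiment 3, names two primary outcomes: maximum FDI force, and FDI activation "calculated using the root-mean-square of EMG signals obtained during FDI contractions". The model has "fixed effects of condition and time point, random intercept of subject". It gives no unit, normalisation or log scale, and no session term, baseline covariate or condition-by-time interaction.

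For Experiment 2 the primary outcome is "amplitude of FDI muscle response after TST application during brain states reflecting strong, weak, and random corticospinal tract recruitment", and the area under that response is secondary. "Both outcomes will be evaluated using linear mixed-effects models (fixed effect of state, random intercept of subject) with alpha equal to 0.05".

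Section 11 (Procedure Description) lists the Experiment 3 steps under Days 1-4, at least 24 hours apart, with EMG electrodes attached each day and one target brain state per session. It adds: "Electrode positions may be marked on the skin using a skin-safe surgical marker to ensure consistent electrode placement across sessions". On the same days, "The M-max following PNS at the wrist will be determined by increasing stimulation intensity until a larger response cannot be obtained". Experiment 2 does the same at the wrist and Erb's point. However, the abbreviation list at the end of Section 3 defines M-max as a stimulation intensity, not a response amplitude, and EMG recording at that step is optional and for quality control. Section 4 provides measurements before PCMS and at 0, 20 and 40 minutes after it in each session.

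**The concern.** Surface EMG amplitude depends on where the electrodes sit. In Experiment 3 condition and electrode placement change together from day to day, and marking positions is optional. Gain multiplies the RMS value, so a day with high gain looks like a day with high activation. With only a subject intercept, nothing in the written model separates the two. The comparison at stake is strong against weak or random states on a primary outcome.

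The Experiment 2 question is different. Hypothesis 2 is about how many motoneurons TMS activates, but an unscaled amplitude also carries muscle size and electrode placement. Participants with large responses weigh more, and the result is not a share of motoneurons.

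**Working it through.** **The plan's own figure.** The target of N=20 (Sections 14 and 15) rests on analogy and gives no effect size, SD or power, so it cannot be reproduced. With 80% power and two-sided alpha 0.05 (sidedness assumed), the detectable paired standardised effect is 0.66 at N=20, 0.81 at N=14 and 0.53 at N=30.

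**How much gain survives a change score.** Let g be session gain (coefficient of variation CV), m the baseline and d the relative effect. The session yields g·m before PCMS and g·m·(1+d) after it. The SD due to gain is CV·m·(1+d) for the post value and CV·m·d for the change. The share of gain variance left is d²/(1+d)²:

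- d = 0.10: 0.01/1.21 = 0.8%
- d = 0.20: 0.04/1.44 = 2.8%
- d = 0.30: 0.09/1.69 = 5.3%
- d = 0.40: 0.16/1.96 = 8.2%

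A raw change or session term therefore removes about 92 to 99%. On the log scale g cancels completely.

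**Experiment 3 simulation.** 4,000 runs, N=20, four conditions, four time points. Assumed, not in the documents: gain CV 0 to 30%, within-session CV 8%, between-participant log SD 0.30, M-max measurement CV 5%, SD of the session-level response 0.05.

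False rejection when strong and weak states both give 10%:

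| Analysis | CV 0 | 10% | 20% | 30% |
|---|---|---|---|---|
| Written model, condition main effect, unscaled | 9.5% | 28% | 37% | 39% |
| Same, EMG/M-max | 19% | 19% | 18% | 18% |
| Change contrast, session term, unscaled | 6% | 6% | 7% | 6% |

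Power of the change contrast, strong 20% against weak 10%:

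| Analysis | CV 0 | 10% | 20% | 30% |
|---|---|---|---|---|
| Subject intercept only, unscaled | 76% | 47% | 6% | 0% |
| Subject intercept only, EMG/M-max | 75% | 76% | 74% | 74% |
| Session term, unscaled | 80% | 81% | 77% | 73% |
| Session term, log EMG | 80% | 81% | 79% | 79% |
| Session term, EMG/M-max (not logged) | 85% | 85% | 84% | 84% |

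The collapse in the first power row is a standard-error problem. At CV 20% the contrast's true SD is 0.041, but the model, with session variance in its residual, reports 0.086. That row also adds an interaction that the plan does not write.

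With a session term, scaling adds 4 to 11 points on the unlogged scale. On the log scale it adds nothing to the change contrast, because M-max is constant within a session: log(post/M) − log(pre/M) = log(post) − log(pre).

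**Experiment 2.** All states share a session and an electrode placement. With an assumed 10% state effect and 10% per-state CV, unscaled power is 78/76/77/75% at gain CV 0/10/20/30%, against 80 to 82% after scaling. Separately, if the effect is proportional to M-max, with between-participant CV c, the standardised effect becomes 0.66/√(1 + c² + 0.66²c²). For c = 0.5 this is 0.66/√1.359 = 0.57. Power falls from 80% to 78, 75, 71 and 67% at c = 0.2, 0.3, 0.4 and 0.5. That loss comes from differences between participants, not from day-to-day gain.

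**The case against.** The case against is substantial.

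- A reader might infer that gain survives any baseline or session term. It does not: such terms remove nearly all of it. In a repeat simulation the unscaled change contrast lost about 10 points at gain CV 30% (77% to 67%) and the log contrast lost none.
- A reader might infer that the sponsor will analyse unscaled microvolts. The documents never say so. They say that EMG is processed offline, and the TST follows a cited procedure that may carry its own scaling.
- A reader might extend the day-to-day problem to Experiment 2, or to all primary outcomes of Experiment 3. In Experiment 2 the states share an electrode placement, and in Experiment 3 force is not an EMG measure.
- M-max has its own error. With 10% error the benefit vanished at gain CV 10% under the subject-intercept model. With baseline as a covariate, which neither the plan nor the fix below uses, power after scaling was 84% at 5% error, 77% at 10% and 68 to 69% at 20%. Unscaled power at gain CV 10% was 76 to 78%.
- Skin marking may keep gain variation small, and the documents give no basis for a CV of 20 to 30%.

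All of this limits the point. It does not dispose of it: the plan contains no session term, change score, log scale or scaling, so none of these remedies protects the analysis as written, and the scale of a primary outcome is left open.

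**Conclusion.** The point holds in limited form and should be acted on. In Experiment 3 day-specific gain enters the condition comparison under the written model. The larger defect is the missing session term and condition-by-time contrast; the unspecified scale comes second. M-max scaling helps greatly only under the subject-intercept model. With a session or change term it adds roughly 0 to 12 points, and it does not by itself repair the condition main-effect test. In Experiment 2 the case is a match to Hypothesis 2 and a small gain in precision, about 2 to 7 points in the simulation (for example 78% to 81% without gain variation and 75% to 82% at CV 30%), of which day-to-day gain accounts for about 1 to 3. Every power figure rests on assumed CVs and effects.

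**What to change.** In Section 5:

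1. Define FDI activation as RMS EMG divided by the same-session, pre-PCMS maximal M-wave amplitude. In Experiment 3, analyse it with a subject-by-session random intercept and a condition-by-time contrast, preferably on the log scale. The session term and contrast do the repair; the division supplies a comparable unit.
2. Define TST amplitude and area as percentages of the same-session maximal FDI response to PNS, amplitude to amplitude and area to area.
3. Require the maximal M response to be recorded and stored in every session, and distinguish this amplitude from M-max as an intensity.
4. Report unscaled results as a sensitivity analysis.

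The cost is a revised outcome definition, one division per session, one extra model term and mandatory storage of a signal already elicited. No stimulation is added. The downside is that error in M-max is carried into the outcome, and the benefit shrinks or vanishes if that error is as large as the day-to-day gain variation.

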hand muscle activation, (c) voluntary hand muscle force production, and (d) hand dexterity more than identical PCMS applied during brain states reflecting weak corticospinal tract recruitment or random brain states.

3 Study Background

To input text, click in the light grey area below.

Stroke is the leading cause of long-term disability in the United States (Go et al. 2013) and commonly disrupts the corticospinal tract (Twitchell 1951). The presence of residual corticospinal connections is one of the best prognostic markers of post-stroke motor function and recovery potential (Stinear et al. 2007), indicating that the most serious and long-lasting stroke-related motor deficits are caused by corticospinal tract disruption. Interventions capable of strengthening residual corticospinal connections are thus promising candidates for improving motor function after stroke. Paired cortico-motoneuronal stimulation (PCMS) can strengthen corticospinal connections in healthy adults (Taylor and Martin 2009; Bunday and Perez 2012) and patients with corticospinal tract disruption caused by spinal cord injury (Bunday and Perez 2012). PCMS involves repeatedly delivering precisely-timed pairs of non-invasive peripheral stimuli (via transcutaneous peripheral nerve stimulation) and cortical stimuli (via transcranial magnetic stimulation) such that they induce long-term potentiation via spike-timing dependent plasticity (STDP_{LTP}) at corticospinal-motoneuronal synapses, which are essential to human dexterity (Lemon 2008).

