Real-time EEG analysis: The EEG system will stream data in real-time to a dedicated computer. This computer will analyze the data in real time to identify brain states associated with strong or weak corticospinal tract recruitment (see above), or a random mixture of the two. When desired states are identified, either a single TMS pulse (see *Evaluation of state-targeting* accuracy) or the TST (see *TST assessment*) will be triggered. *Evaluation of state-targeting accuracy:* <= 150 single TMS pulses will be applied to the scalp at <= 120% of scalp RMT during EEG recordings.

Calculation of ISIs for TST assessment: The following stimulation procedures will be performed to calculate the ISIs for TST assessment.

- 1. <= 25 Single-pulse TMS to the scalp at <= 120% of scalp RMT
- 2. <= 25 Single-pulse PNS to the left wrist at <= 120% of M-max
- 3. <= 25 Single-pulse PNS to the left Erb's point at <= 120% of M-max

TST assessment: The TST will be applied according to an established protocol (Magistris et al. 1998) using consecutive application of TMS (<= 120% of scalp RMT), PNS at the left wrist (<= 120% of M-max), and PNS at the left Erb's point (<= 120% of M-max). The delays between each stimulus will be individualized based on each participants central and peripheral conduction times (see *Calculation of ISIs for TST assessment*). The TMS portion of the TST will be timed to occur during brain states reflecting strong corticospinal tract recruitment, weak corticospinal tract recruitment, or random brain states, using real-time EEG analysis. <= 50 TST applications will be performed per brain state condition.

Experiment 3

Design: within-subjects, single group Population: healthy adults (≥ 18 years old)

Conditions: At least 24 hours will elapse between sessions.

- 1. Active PCMS delivered during brain states reflecting strong corticospinal recruitment
- 2. Active PCMS delivered during brain states reflecting weak corticospinal recruitment
- 3. Active PCMS delivered during random brain states

- 4. Control PCMS delivered during brain states reflecting strong corticospinal recruitment
 - a. The order of conditions will be counterbalanced
 - b. Participants may complete one, two, three or four of the conditions

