- The TST will be applied during brain states reflecting strong corticospinal recruitment, brain states reflecting weak corticospinal recruitment, and randomly selected brain states according to an established procedure (Magistris et al. 1998), with details below. EMG data will be recorded and processed offline to calculate the primary and secondary outcomes. EEG data will be recorded and processed offline to ensure accurate state identification as a quality control procedure (Zrenner et al. 2018; [name] et al. 2020).
 - TMS will be timed using the real-time EEG analysis algorithm
 - After an interstimulus interval equal to delay 1, Wrist PNS will be applied.
 - After an interstimulus interval equal to delay 2, Erb's point PNS will be applied.
- The EEG cap, EMG electrodes, and PNS electrodes will be removed and participants will leave the laboratory.
- If participants are asked to complete two sessions, the same experimental procedures described above may be used during the second session. The second session may be used to evaluate between-day reliability of the measurements made during the first session. At least 24 hours will elapse between sessions.

Experiment 3

Days 1-4 (at least 24 hours will elapse between sessions)

- The participant and research team member will review and discuss the informed consent document.
- Eligibility will be formally determined by the research team member by reviewing a list of the inclusion and exclusion criteria verbally with the participant (see attachments).
- Participants will complete a short demographics survey.
- The skin on the left hand and wrist will be cleaned using isopropyl alcohol. EMG electrodes will be attached to a maximum of 5 hand and wrist muscles using medical grade adhesive. PNS electrodes will be attached to the left wrist using medical grade adhesive. A ground electrode will also attached to the dorsum of the hand in the same manner.
- The scalp TMS hotspot will be determined as the site of the scalp producing the most reliable focal muscle twitch within the left first dorsal interosseous muscle. The scalp RMT will be determined using an automatic threshold tracking tool (Awiszus and Borckhardt 2011) as the minimum stimulation intensity needed to elicit a MEP of 50 microvolts in peak-to-peak amplitude in response to 50% of stimuli. EMG signals may be recorded for offline quality control analysis.

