 - Active PCMS during brain states reflecting weak corticospinal recruitment, with the delay between scalp TMS and wrist PNS equal to the Active PCMS delay.
 - Active PCMS during random brain states, with the delay between scalp TMS and wrist PNS equal to the Active PCMS delay.
 - Control PCMS during brain states reflecting strong corticospinal recruitment, with the delay between scalp TMS and wrist PNS equal to the Control PCMS delay.
- Participants will complete post-PCMS measurements of corticospinal excitability, spinal excitability, voluntary motor output, and manual dexterity (see Design and Methodology) immediately, 20 minutes, and 40 minutes after PCMS is complete. EMG signals will be recorded during all measurements and processed offline to obtain outcome measures. EEG may recorded for offline quality control analysis.
- EEG, EMG and PNS electrodes will be removed and participants will leave the laboratory.

SUBJECT POPULATION

12 Protected Subject Populations

Click on the check box (or double click and type an "X" if using Google Docs) each population, if they are specifically studied for this research.

13* Research Participant Information

Describe the research population.

*For multiple research populations (e.g., teachers, students, and parents), copy this section as necessary to describe your population.

a Participant Group Name

To input text, click in the light grey area below. Healthy adults

b Minimum Age

To input text, click in the light grey area below. 18

c Maximum Age

To input text, click in the light grey area below. none

d Inclusion Criteria

To input text, click in the light grey area below. Right-hand dominance Willingness to participate

Ability to provide informed consent

e Exclusion Criteria

To input text, click in the light grey area below.

History of major neurological, orthopedic, psychiatric, or cardiovascular disease Presence of contraindications to TMS or PNS (Keel et al. 2000), including:

- 1) history of adverse reactions to TMS or PNS
- 2) history of stroke or head injury
- 3) metal in head, eyes, neck, chest/trunk, or arms, including but not limited to shrapnel, surgical clips, fragments from metalworking, fragments from welding
- 4) implanted devices
- 5) history of frequent and severe headaches or migraines
- 6) immediate family history of seizure or epilepsy
- 7) personal history of seizure or epilepsy
- 8) current, suspected, or planned pregnancy

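### The only dexterity score, pegs placed per attempt on a nine-hole board, has no attempt window or refill rule; unless attempts are cut short or pegs are replaced, healthy adults have little room to improve on it.

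*Combined protocol and SAP*

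**What the plan says.** Section 2 expects PCMS given in strong-recruitment states to improve, as its last component, "d) hand dexterity more than identical PCMS applied during brain states reflecting weak corticospinal tract recruitment or random brain states". Section 5 (Data Analysis, Experiment 3) gives that component a single measure: "Secondary outcome: Number of pegs placed per attempt at the 9-hole Pegboard test".

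Section 4 (Design and Methodology, Experiment 3) describes the test only as "<= 5 attempts of the 9-hole peg test", done before PCMS and 0, 20 and 40 minutes after it. The sentence before it does give a duration for the other behavioural measure: "<= 5 maximum voluntary contractions of the FDI, each lasting <= 5 seconds". Section 11 refers back to section 4 for dexterity, and section 40 merely names the test. None of these places gives an attempt window, a stopping or refill rule, or a completion time, and no source is cited for the test.

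The tested hand is not named for this test, but the left is strongly implied. The abbreviation list defines FDI as the left muscle. Section 11 prepares the left side ("The skin on the left hand and wrist will be cleaned using isopropyl alcohol"). It also says, where it lists the dexterity measurement, that "EMG signals will be recorded during all measurements and processed offline to obtain outcome measures". Since section 13 requires "Right-hand dominance", this would be the non-dominant hand.

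**The concern.** A nine-hole board has a natural maximum. If pegs are not replaced during an attempt, the count cannot exceed 9, and everyone who fills the board gets 9 however quickly they do it. The participants are healthy adults screened for major neurological and orthopedic disease. If attempts are untimed or generously timed, most will probably score 9 or close to it before PCMS. A real gain in speed would then leave no trace in the score.

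Because no other outcome addresses Hypothesis 3(d), a null dexterity result could not be told apart from a score with no room to move. The planned linear mixed model makes no provision for a bounded count.

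**Working it through.** **The plan's own figure.** Section 14 sets a target of 20 (maximum 30) for Experiment 3. Section 15 reaches 20 by raising a previous N of 14. It gives no effect size, SD or power, and nothing specific to the peg test, so the figure cannot be reproduced for this outcome. For context, a two-sided paired t-test at 0.05 with 80% power detects a standardized difference of about 0.66 with 20 pairs and 0.81 with 14.

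**Inputs from the documents.** Nine holes; up to 5 attempts per time point; target N=20; alpha 0.05.

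**Assumptions (none is in the documents).**
- T, the time to place nine pegs relative to its mean, is lognormal with mean 1.
- Three spreads, as CV between subjects / between blocks / between attempts: 10/3/6%, 15/5/10% and 25/5/10%.
- PCMS shortens T by 10% in one condition and by nothing in the other.
- All 5 attempts are done and averaged, and all 20 participants complete both conditions.
- W, the attempt window in multiples of the mean nine-peg time, is varied.

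**Scores.**
- Capped count (no refill): min(9, floor(9W/T)).
- Refilled count: floor(9W/T).
- Completion time: T.

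**One typical attempt.** T falls from 1.0 to 0.9.
- W=0.8: 9×0.8/1.0 = 7.2, score 7; 9×0.8/0.9 = 8.0, score 8. The gain shows.
- W=1.25: 9×1.25/1.0 = 11.25 and 9×1.25/0.9 = 12.5. The refilled count goes from 11 to 12; the capped count stays at 9.

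**Power.** The contrast is (post − pre) with the gain minus (post − pre) without it, by two-sided one-sample t-test at 0.05, with 10,000 simulated trials per cell. Samples with no variance count as not significant. Ranges cover the three spreads.

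| W | Baseline attempts at 9 | Power, capped count |
|---|---|---|
| 0.8 | 4–25% | 0.81–1.00 |
| 1.0 | 52–55% | 0.56–0.92 |
| 1.25 | 83–97% | 0.02–0.18 |
| 1.5 | 95–100% | at most 0.02 |
| 2.0 | over 99% | 0.00 |

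Completion time gives 0.88–1.00. The refilled count gives 0.89–1.00 at every window from 0.6 to 2.0.

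**Sensitivity.**
- *5% gain:* completion time 0.34–0.76, refilled count 0.33–0.77, capped count at W=1.25 at most 0.08.
- *Only 10 complete pairs, 10% gain* (section 4 says "Participants may complete one, two, three or four of the conditions"): completion time 0.56–0.95, capped count at W=1.25 at most 0.04.
- *Four conditions, four time points, random intercept, N=20, 10% gain, 3,000 trials:* completion time 0.98–1.00; capped count 0.15–0.37 at W=1.25, 0.01–0.16 at 1.5 and at most 0.04 at 2.0. This uses a condition-by-time term, which is an assumption because section 5 lists only the two fixed effects. No multiplicity correction is applied.
- *Times in seconds:* a separate single-condition pre–post model assumed a median nine-peg time of 8 to 15 s and a 5% gain. With a 20 s window, 95.5–100% of baseline attempts score 9 and power is at most 0.03. With a 12 s nine-peg time and an 8 s window, the baseline mean is 5.6 pegs, about 1% are at the cap and power is about 0.96.

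**The case against.** The strongest reply is that a peg count makes sense as an outcome only if attempts end before the board is full or pegs are replaced. Choosing it therefore hints that such a rule exists in the laboratory and was left out of the form. On that view, the documents show incomplete operational detail, not an insensitive outcome. With a capped count and windows of 0.6 to 0.7, power is 0.86–1.00, about the same as for completion time. This stands: a reader might infer that dexterity scores will sit at 9, but the documents contain no peg times, pilot scores or window to show that.

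The comparison with the timed contractions is also weak evidence. The form habitually sets upper limits on exposure, and a missing limit for pegs does not mean that attempts are untimed.

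A reader might also infer that the tested hand is unknown. That is too strong, since section 11 and the abbreviation list point to the left; a short clarification is enough. If it is the left hand, a perfect baseline score is somewhat less certain, because that hand is non-dominant and carries electrodes.

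Finally, the power figures come from scenarios and run from 1.00 to 0.00 depending on an unknown window. They show where the score stops working, not what this trial's power is.

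What the reply does not remove is the gap in the text. Followed literally, the protocol lets a completed attempt score 9 at any speed, and timing it gives a score without that limit.

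**Conclusion.** The point holds in conditional form. The sole outcome for Hypothesis 3(d) lacks the rule that determines whether it can register improvement. If pegs are not replaced and the window is about 1.25 times the mean nine-peg time or longer, the two-condition contrast has power below 0.2 for a 10% gain, against about 0.9 to 1.0 for completion time or a refilled count. With a window clearly shorter than the nine-peg time, or with refill, the problem largely disappears. These sizes rest wholly on the assumed spreads, gain and number of attempts. Completion time does not guarantee power either: for a 5% gain it reaches only 0.34–0.76.

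It would be wrong to extend this to Experiment 3 as a whole. Force and FDI activation, the primary outcomes, and the exploratory MEP and F-wave measures do not depend on the peg score. The change is worth making, at the weight of a secondary outcome.

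**What to change.** - Record the completion time in seconds for every peg-test attempt already scheduled.
- Make completion time the secondary dexterity outcome in the planned mixed model, and keep pegs placed as a descriptive measure.
- State that the left hand is tested, if that is intended.
- If a short fixed window or a refill rule is already in use, the count may stay as the outcome once the protocol states the window and the rule.
- Make the choice before anyone looks at results by condition.

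The cost is a stopwatch reading per attempt and a small IRB amendment, or one or two sentences if a window or refill rule already exists. No extra attempts or participants are needed. The drawback is that any sessions already run without timing would have only the count.
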